9.2 INCLUSION CRITERIA

Subjects will be considered qualified for enrollment if they meet the following criteria:

1. Subject has undergone arthroscopic or open soft tissue repair with Q-Fix™ All-Suture Anchor System
2. Subject was ≥ 13 of age at time of surgery

9.3 EXCLUSION CRITERIA

Any one (1) of the following criteria will disqualify a potential subject from participation in the study:

1. Subject is ≤ 6 months post-operative
2. Subject is entered in another investigational drug, biologic, or device study or has been treated with an investigational product within 12 months post-operative.

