Number of Study Sites:	Approximately 3 sites for each joint indication: up to 9 sites total								
Targeted Global Regions:	United States (US)								
Inclusion Criteria:	
 1. Subject has undergone arthroscopic or open soft tissue repair with Q-Fix™ All-Suture Anchor System 2. Subject was ≥ 13 of age at time of surgery 								
Exclusion Criteria:	
 1. Subject is ≤ 6 months post-operative 2. Subject is entered in another investigational drug, biologic, or device study or has been treated with an investigational product within 12 months post-operative. 								
Study Duration:	
The expected timeline for the study is a total of approximately 2.5 years:
 
 • 6 months for site initiation • 16 months for subject enrollment • 2 months for follow-up • 6 months to analyze the data and prepare the final study report. 								

CONFIDENTIAL AND PROPRIETARY

This document contains information that is confidential and proprietary to Smith & Nephew PLC and Smith & Nephew, Inc. and is intended for use only by Smith & Nephew and its manufacturer. It shall not be reproduced or copied in whole or in part, nor shall the contents be disclosed by any means without prior written permission from Smith & Nephew, nor shall anyone make any use of it that is contrary to the expressed or implied wishes of Smith & Nephew.

Study Protocol—Device	
Safety and Performance of Q-Fix™ All-Suture Anchor System	Number: 17-5010-11
	Version: 2.0 05SEP2019
	Page: Page 6 of 62

Primary endpoint:	
 • Clinical success rate, defined as subjects without re-intervention at 6 months post-operative, as assessed by the surgeon
Secondary endpoints:	
 • Clinical success rate, defined as subjects without re-intervention at 12 months post-operative, as assessed by the surgeon • Visual Analog Scale (VAS) - pain • Range of Motion (ROM) • Clinical success rate in adolescents and young adults, defined as subjects ages 13-21 years of age without re-intervention at 6 and 12 months post-operative
Safety Endpoints:	
 • Device-related re-intervention • All adverse events (AEs) occurring from the time of surgery until revision or study completion • Device related AEs and serious adverse events (SAE's)

CONFIDENTIAL AND PROPRIETARY

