9. SUBJECT ENROLLMENT AND WITHDRAWAL

9.1 SUBJECT POPULATION

To eliminate the potential for bias, Investigators will consecutively screen subjects by date of surgery, starting with subjects that have undergone arthroscopic or open soft tissue repair with Q-Fix™ All-Suture

CONFIDENTIAL AND PROPRIETARY

This document contains information that is confidential and proprietary to Smith & Nephew PLC and Smith & Nephew, Inc. and is intended for use only by Smith & Nephew and its manufacturer. It shall not be reproduced or copied in whole or in part, nor shall the contents be disclosed by any means without prior written permission from Smith & Nephew, nor shall anyone make any use of it that is contrary to the expressed or implied wishes of Smith & Nephew.

Study Protocol—Device	
Safety and Performance of Q-Fix™ All-Suture Anchor System	Number: 17-5010-11
	Version: 2.0 05SEP2019
	Page: Page 19 of 62

Anchor system in the past 12 months as of the IRB approval date, or using another date as agreed upon by the Investigators and site. In addition, to ensure enrollment of Q-Fix™ MINI subjects, a different enrollment start date may be selected to enroll Q-Fix™ MINI subjects only.

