9.8 WITHDRAWAL

9.8.1 Conditions for Study Termination

All reasonable efforts should be made to collect 12 month postoperative data on all subjects enrolled in this study. There are multiple reasons a subject may be terminated from the study. For each case, information will be obtained on the End of Study CRF, detailing circumstances leading to the withdrawal.

9.8.1.1 *Voluntary Withdrawal*

CONFIDENTIAL AND PROPRIETARY

This document contains information that is confidential and proprietary to Smith & Nephew PLC and Smith & Nephew, Inc. and is intended for use only by Smith & Nephew and its manufacturer. It shall not be reproduced or copied in whole or in part, nor shall the contents be disclosed by any means without prior written permission from Smith & Nephew, nor shall anyone make any use of it that is contrary to the expressed or implied wishes of Smith & Nephew.

Study Protocol—Device	
Safety and Performance of Q-Fix™ All-Suture Anchor System	Number: 17-5010-11
	Version: 2.0 05SEP2019
	Page: Page 22 of 62

Study participation is voluntary and subjects may withdraw from the study without giving reason for doing so.

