##### 5.2 Secondary Endpoints

- Clinical success rate, defined as subjects without re-intervention at 12 months post- operative, as assessed by the surgeon
- Visual Analog Scale-pain
- ROM
- Clinical success rate in adolescents and young adults, defined as subjects ages 13-21 years of age without re-intervention at 6 and 12 months post-operative

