#### 7.4.2 Derived Data for the Secondary Endpoints

The final count of re-interventions for the 12 month post-operative time point will be defined as any revision that occurred between the end of the 6 Month window (273 days) and the end of the 12 Month window (456 days) i.e. if (273 days <= Date of Revision – Date of Surgery <= 456 days).

Where the Date of Revision is obtained from the Implant Revision CRF and the Surgery Date is obtained from the Operative Data CRF.

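### The plan does not say how an event-free subject whose record ends before the 6- or 12-month time point enters the success rate

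*Protocol*

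**What the plan says.** - **Entry.** Protocol 9.3 excludes a potential subject if "Subject is ≤ 6 months post-operative". No longer minimum is set.
- **Timeline.** The Protocol Synopsis lists "16 months for subject enrollment", then "2 months for follow-up".
- **Surgery dates.** Protocol 9.1 starts consecutive screening with surgeries "in the past 12 months as of the IRB approval date, or using another date as agreed upon by the Investigators and site". It allows a different start date for MINI subjects. The rationale in Protocol 23.3 says that date will be more recent.
- **Endpoint.** SAP 5.2 gives the 12-month endpoint as "Clinical success rate, defined as subjects without re-intervention at 12 months post- operative, as assessed by the surgeon". SAP 5.1 has the same form at 6 months.
- **Derivation.** SAP 7.4.1 counts revisions fewer than 273 days after surgery. SAP 7.4.2 counts "any revision that occurred between the end of the 6 Month window (273 days) and the end of the 12 Month window (456 days").
- **Incomplete records.** SAP 7.3 plans no imputation and limits analysis to observed data. SAP 7.2 removes subjects lost to follow-up or dead from the per-protocol set, and its list is open-ended. SAP 7.6 tabulates subjects whose visit window is still open (Not Yet Overdue), for disposition only. Protocol 9.8.1 adds: "All reasonable efforts should be made to collect 12 month postoperative data on all subjects enrolled" in the study.

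**The concern.** A success here is the absence of a dated event. That absence is informative only if the record is known to run to the time point. SAP 7.4.1 and 7.4.2 ask whether a revision date falls in an interval. They do not ask how far the record extends.

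A subject with a short, event-free chart therefore has no missing value for SAP 7.3 to act on. Such a subject need not be lost to follow-up either, because Protocol 9.7 defines that as not returning under the investigator's own standard of care. Two programmers could build different denominators and both claim to follow the SAP.

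The choice affects the 12-month rate, the rates at ages 13 to 21 and the rates by anchor size. It affects the 6-month rate to a lesser degree.

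**Working it through.** **Inputs from the documents:** entry after more than 6 months (about day 183); 16 months of enrolment and 2 months of follow-up (about 61 days); count limits at days 273 and 456; 12-month window 365 ± 91 days, so it opens at day 274; assumed success 95%; 5% loss; exact 95% CI.

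**Assumptions:** constant hazard, and the distributions of surgery and chart-review dates stated below.

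**1. The plan's own figure.** 28/0.95 = 29.5, rounded up to 30 per joint; × 3 = 90, as stated. The exact 95% CI at 95% success with n = 84 is 87.9% to 98.6%, a full width of 10.6 points, which matches the stated 11% as a full width. The 5% allowance covers loss to follow-up. Nothing is allowed for windows that are still open.

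**2. Shortest record at study end.** 183 + 61 = 244 days. This is short of day 273 by 29 days, of day 274 by 30, of day 365 by 121 and of day 456 by 212.

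**3. How many could be short.** Take the least favourable entry pattern: everyone enters at day 183, evenly over 16 months, and charts are read to study end. The share not reaching day d is ((d − 183)/30.44 − 2)/16. That is 6% for day 274, 25% for day 365 and 44% for day 456.

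**4. Direction of bias.** Let true success at day 456 be 95%, and let a share u of subjects be seen only to day 244. Their failure by then is 1 − 0.95^(244/456) = 2.7%. With u = 25%:
- Observed failures are 0.75 × 5% + 0.25 × 2.7% = 4.43% of all subjects.
- If short event-free subjects count as successes: 100 − 4.43 = **95.6%**.
- If they are dropped but all failures are kept, the denominator is 0.75 + 0.25 × 0.027 = 0.757, giving 1 − 0.0443/0.757 = **94.2%**.
- Kaplan-Meier with censoring at day 244 recovers 95%, because censoring here does not depend on outcome.

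**5. Size of the upward reading under the default frame.** Let failure be 5% by day 273, so h = −ln(0.95)/273 = 0.000188 per day. True cumulative failure from surgery to day 456 is 1 − exp(−456h) = 8.2%. Observed failure is the mean of 1 − exp(−h × min(t, 456)), where t is days from surgery to end of record. Surgeries are uniform over 183 to 365 days before IRB approval.

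| Chart review | Short of day 273 | Observed failure | Success overstated by |
|---|---|---|---|
| All at IRB approval, nothing added | 49.5% | 5.0% | about 3 points |
| All at IRB approval, plus 61 days | 16% | 6.1% | about 2 points |
| Spread evenly over 16 months, nothing added | 4.6% | 7.6% | 0.6 points |
| Spread evenly over 16 months, plus 61 days | 0.5% | 7.9% | 0.3 points |

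Spreading the reviews is closer to the planned timeline. For scale, the exact half-width at 95% success is 5.3 points with 84 subjects and 2.1 points with 450.

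**The case against.** The strongest reply is that the SAP already permits exclusion. SAP 7.3 restricts analysis to observed data, SAP 7.2 leaves the per-protocol removals open-ended, SAP 7.7 treats missed or out-of-window visits as deviations to be settled before database lock, and SAP 7.6 identifies open windows. This is fair as far as it goes. A reader might infer that the plan counts unobserved subjects as 12-month successes, but no passage says so; it is only the default result of coding by revision date. These passages permit exclusion without requiring it. Excluding only the event-free subjects would exchange an upward bias for a downward one.

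A reader might also take the 2 months as a limit on each subject's follow-up. It is a study phase after enrolment closes, so early entrants could be followed for up to about 18 months (16 + 2). The 2 to 3 point figures need every chart to be read at IRB approval, and the timeline does not suggest that.

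Other text points to more mature records. Protocol 9.5 directs the consent waiver to subjects who have completed a 12-month visit, have died or are lost. Protocol 23.3 reports 106 + 99 + 24 = 229 subjects already enrolled. On the other side, data are collected only as far as they are available (Protocol Table 1, footnote 1), so a chart may end well before the review date.

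For the primary endpoint the point is weaker. Every subject has passed 6 months by eligibility, and the shortfall is against the SAP's day-273 limit.

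**Conclusion.** The gap is real and should be closed before database lock. Records can end before day 273, day 365 or day 456, and no rule fixes how an event-free subject is then handled. Both obvious readings mis-estimate the rate: 95.6% or 94.2% against a true 95% when a quarter of subjects are seen only to day 244.

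Under the default surgery frame with reviews spread over 16 months, the upward reading overstates day-456 success by about 0.3 to 0.6 points. That is small beside the planned precision. These sizes rest on a constant hazard, 5% failure by day 273 and assumed surgery dates; the documents supply no dates to replace the last assumption.

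The effect could be larger for MINI subjects if their start date is more recent. It would go too far to say that the anchor-size results favour MINI: Protocol 9.1 says only that the date may differ, and the by-size analysis is exploratory, with no test between sizes.

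**What to change.** In SAP 7.4.1, 7.4.2 and 7.9.1 to 7.9.3:

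1. Record the date of last chart contact for each subject.
2. Estimate the re-intervention-free rate by Kaplan-Meier, censored at that date, with a log-log 95% CI, at pre-specified days that match the 6- and 12-month endpoints.
3. Count all revisions from surgery. SAP 7.4.2 now starts its count at day 273, so the 12-month estimate should state that earlier revisions are included.
4. Show numbers at risk by joint and anchor size.
5. Keep the exact binomial proportion as a supporting summary. It also serves where a subgroup has no revisions and the log-log interval cannot be computed. At 95% success and 28 subjects, that has probability 0.95^28 = 24%.

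Do not restrict the denominator by keeping every failure while dropping short event-free subjects; step 4 of the working shows the downward bias.

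The cost is SAP wording, a slightly wider 12-month interval, and one date field if it is not already on the CRF. Kaplan-Meier also assumes that the end of a chart is unrelated to the risk of re-intervention, and the report should state this.

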9.4 SCREENING

Participating study sites are required to document all screened subjects considered for inclusion in this study. If a subject is excluded from the study, the reasons for exclusion will be documented in the subject's source documents and noted on the Screening and Enrollment Log.

If during screening, a subject is found to have had re-intervention of the Q-Fix™ All-Suture Anchor system, the subject is still eligible to be enrolled in the study. Site staff will complete an End of Study Case Report Form (CRF) for all subjects who do not finish the study, documenting the reason for withdrawal.

CONFIDENTIAL AND PROPRIETARY

This document contains information that is confidential and proprietary to Smith & Nephew PLC and Smith & Nephew, Inc. and is intended for use only by Smith & Nephew and its manufacturer. It shall not be reproduced or copied in whole or in part, nor shall the contents be disclosed by any means without prior written permission from Smith & Nephew, nor shall anyone make any use of it that is contrary to the expressed or implied wishes of Smith & Nephew.

Study Protocol—Device	
Safety and Performance of Q-Fix™ All-Suture Anchor System	Number: 17-5010-11
	Version: 2.0 05SEP2019
	Page: Page 20 of 62

9.5 INFORMED CONSENT

Study sites will obtain Institutional Review Board (IRB) approval for this study.

An IRB waiver of informed consent for study participation should be requested for those subjects who meet eligibility criteria and have retrospectively completed a 12 month postoperative visit, are deceased, or are lost to follow-up, per IRB policy. If allowed, a retrospective data set will be collected on these subjects. A copy of the waiver of informed consent will be placed in the subject file.

A waiver or alteration of the requirements for obtaining informed consent can occur under any of the following three provisions set forth by the Department of Health and Human Health Services:

- Research in general: an IRB may waive or alter the requirement of informed consent under 45 CFR 46.116(d), provided that the IRB finds and documents that all of the following four conditions are met:
 1. the research involves no more than minimal risk to the participants;
 2. the waiver or alteration will not adversely affect the rights and welfare of the participants;
 3. the research could not practicably be carried out without the waiver or alteration; and
 4. Whenever appropriate, the participants will be provided with additional pertinent information after participation.

If an IRB waiver is not granted, then the informed consent shall be obtained from all study subjects according to ISO 14155 guidelines and all applicable national regulations. Potential subjects must be informed as to the purpose of the study and the potential risks and benefits known or that can be reasonably predicted or expected as described in the written consent form. The subject, or their legally authorized representative, will then **read, sign, and personally date** the IRB approved informed consent document(s) (see below for difficulties with reading and writing). If the subject is an adolescent ages 13-17 years old, a signed adolescent informed consent form will be required of the subject as well as a

CONFIDENTIAL AND PROPRIETARY

This document contains information that is confidential and proprietary to Smith & Nephew PLC and Smith & Nephew, Inc. and is intended for use only by Smith & Nephew and its manufacturer. It shall not be reproduced or copied in whole or in part, nor shall the contents be disclosed by any means without prior written permission from Smith & Nephew, nor shall anyone make any use of it that is contrary to the expressed or implied wishes of Smith & Nephew.

Study Protocol—Device	
Safety and Performance of Q-Fix™ All-Suture Anchor System	Number: 17-5010-11
	Version: 2.0 05SEP2019
	Page: Page 21 of 62

signed parental informed consent form of a parent or guardian. Additionally, the individual who obtains consent from the subject will sign and date the informed consent document. A copy of the signed informed consent documentation will be provided to the subject, a copy will be placed in the subject's medical record, and the original filed in the Investigator Site File (ISF).

If a subject refuses participation, no further information will be collected. Reason for exclusion should be noted on the Screening and Enrollment Log.

9.6 ENROLLMENT

Enrollment in this study shall occur when subjects have met inclusion criteria and none of the exclusion criteria.

For screening, only information in the medical records will be reviewed. Once a subject has completed the informed consent process, if required by the IRB, or a waiver of consent is granted, the subject will be considered enrolled and assigned a consecutive Subject Identification (ID) number.

9.7 LOST TO FOLLOW-UP

A subject will be considered lost to follow-up if he/she did not return to for follow-up per the study Investigator's standard of care.

9.8 WITHDRAWAL

9.8.1 Conditions for Study Termination

All reasonable efforts should be made to collect 12 month postoperative data on all subjects enrolled in this study. There are multiple reasons a subject may be terminated from the study. For each case, information will be obtained on the End of Study CRF, detailing circumstances leading to the withdrawal.

9.8.1.1 *Voluntary Withdrawal*

CONFIDENTIAL AND PROPRIETARY

This document contains information that is confidential and proprietary to Smith & Nephew PLC and Smith & Nephew, Inc. and is intended for use only by Smith & Nephew and its manufacturer. It shall not be reproduced or copied in whole or in part, nor shall the contents be disclosed by any means without prior written permission from Smith & Nephew, nor shall anyone make any use of it that is contrary to the expressed or implied wishes of Smith & Nephew.

Study Protocol—Device	
Safety and Performance of Q-Fix™ All-Suture Anchor System	Number: 17-5010-11
	Version: 2.0 05SEP2019
	Page: Page 22 of 62

Study participation is voluntary and subjects may withdraw from the study without giving reason for doing so.

9.8.1.2 Study Termination by Investigator/Sponsor

The Investigator **should** withdraw subjects from the study if the Investigator or the Sponsor stops the study for any reason

9.8.1.3 Use of Data Following Withdrawal

In cases where the subject withdraws consent, the data collected up to the point of withdrawal may be used but no additional data for that subject may be collected.

9.8.1.4 Study Site Discontinuation

A specific study site in this multicenter study may also warrant termination under the following conditions:

- non-compliance to Good Clinical Practice (GCP) or protocol
- failure to enroll subjects
- major protocol deviations
- inaccurate or incomplete data
- unsafe or unethical practices
- safety or performance considerations
- investigator involuntarily discontinues participation in study

10. STUDY DESIGN

10.1 STUDY DESIGN

This is a retrospective, multi-center, case series study to collect clinical data that will evaluate post-market Safety and Performance of the Q-Fix™ All- Suture Anchor System in the knee, shoulder and hip.

CONFIDENTIAL AND PROPRIETARY

This document contains information that is confidential and proprietary to Smith & Nephew PLC and Smith & Nephew, Inc. and is intended for use only by Smith & Nephew and its manufacturer. It shall not be reproduced or copied in whole or in part, nor shall the contents be disclosed by any means without prior written permission from Smith & Nephew, nor shall anyone make any use of it that is contrary to the expressed or implied wishes of Smith & Nephew.

Study Protocol—Device	
Safety and Performance of Q-Fix™ All-Suture Anchor System	Number: 17-5010-11
	Version: 2.0 05SEP2019
	Page: Page 23 of 62

A minimum of 90 subjects and a maximum of 450 subjects in the United States who underwent surgery in the knee, shoulder or hip using the Q-Fix™ All- Suture Anchor System are planned to be enrolled into the study after the fulfilment of all inclusion and exclusion criteria.

Data from eligible subjects will have their data recorded on case report forms.

10.2 STUDY ENDPOINTS

10.2.1 Primary Endpoint

- Clinical success rate, defined as subjects without re-intervention at 6 months post- operative, as assessed by the surgeon

10.2.2 Secondary Endpoints

- Clinical success rate, defined as subjects without re-intervention at 12 months post- operative, as assessed by the surgeon
- VAS -pain
- ROM
- Clinical success rate in adolescents and young adults, defined as subjects ages 13-21 years of age without re-intervention at 6 and 12 months post-operative

10.2.3 Safety Endpoints

- Device-related re-intervention
- All adverse events (AEs) occurring from the time of surgery until revision or study completion
- Device related AEs and serious adverse events (SAE's)

CONFIDENTIAL AND PROPRIETARY

This document contains information that is confidential and proprietary to Smith & Nephew PLC and Smith & Nephew, Inc. and is intended for use only by Smith & Nephew and its manufacturer. It shall not be reproduced or copied in whole or in part, nor shall the contents be disclosed by any means without prior written permission from Smith & Nephew, nor shall anyone make any use of it that is contrary to the expressed or implied wishes of Smith & Nephew.

Study Protocol—Device	
Safety and Performance of Q-Fix™ All-Suture Anchor System	Number: 17-5010-11
	Version: 2.0 05SEP2019
	Page: Page 24 of 62

